21. SAFETY OUTCOMES

All outputs for safety outcomes will be based on the Safety Analysis Set (SAF).

Safety and tolerability will be assessed in terms of AEs, laboratory data (haematology, blood chemistry, urinalysis), ECG data, vital signs (heart rate and blood pressure), BMI and weight, which will be collected for all patients.

21.1. ADVERSE EVENTS

All adverse events (AEs) reported on eCRF and experienced by the patient on or after the informed consent date will be considered in the analysis. Thus, there will not be derivation to Treatment-emerged Adverse Events (TEAE) and not TEAE.

Adverse event Investigator terms will be assigned to a Preferred Term (PT) and will be classified by primary System Organ Class (SOC) according to the Medical Dictionary for Regulatory Activities (MedDRA) thesaurus, version 20.0 or higher

Counts and percentages will be presented by primary System Organ Class (SOC) and Preferred Term (PT) as defined in MedDRA thesaurus, by treatment arm.

A patient having more than one AE with the same PT will be counted only once in the incidence calculation for that PT. Similarly, if a patient has more than one AE in the same SOC, the patient will be counted only once in the total number of patients with an AE for that SOC.

An AE will be defined “Related” if causality is “Certain”, “Probable” or “Possible”.

The following frequency distributions of adverse events will be provided by treatment arm:

- An overview of AEs including the number of patients with:
 - at least one AE,
 - at least one non-serious AE,
 - at least one AE related to Ipilimumab,
 - at least one AE related to Nivolumab,
 - at least one AE related to Combo Immuno Therapy,
 - at least one AE related to LGX818,
 - at least one AE related to MEK162,
 - at least one AE related to Combo Target Therapy,
 - at least one serious AE (SAE),
 - at least one SAE related to Ipilimumab,
 - at least one SAE related to Nivolumab,
 - at least one SAE related to Combo Immuno Therapy,
 - at least one SAE related to LGX818,
 - at least one SAE related to MEK162,
 - at least one SAE related to Combo Target Therapy,
 - at least one AE leading to hospitalization,
 - at least one AE leading to withdrawal from the study,

- at least on AESI,
and the number of AEs, non-serious AEs, SAEs, AEs related to Ipilimumab, AEs related to Nivolumab, AEs related to Combo Immuno Therapy, AEs related to LGX818, AEs related to MEK162, AEs related to Combo Target Therapy, SAEs related to Ipilimumab, SAEs related to Nivolumab, SAEs related to Combo Immuno Therapy, SAEs related to LGX818, SAEs related to MEK162, SAEs related to Combo Target Therapy, AEs leading to hospitalization, AEs leading to death, AEs leading to study withdrawal, AESIs;
- AEs presented by Primary SOC and PT;
- AEs related to Ipilimumab presented by Primary SOC and PT;
- AEs related to Nivolumab presented by Primary SOC and PT;
- AEs related to Combo Immuno Therapy presented by Primary SOC and PT;
- AEs related to LGX818 presented by Primary SOC and PT;
- AEs related to MEK162 presented by Primary SOC and PT;
- AEs related to Combo Target Therapy presented by Primary SOC and PT;
- Serious AEs presented by Primary SOC and PT;
- AEs leading to hospitalization presented by Primary SOC and PT;
- AEs leading to death presented by Primary SOC and PT;
- AEs leading to study withdrawal presented by Primary SOC and PT.
- AESIs presented by Primary SOC and PT

The following individual data listings will be produced:

- A listing of all AEs;
- A listing of AEs related to Ipilimumab;
- A listing of AEs related to Nivolumab;
- A listing of AEs related to Combo Immuno Therapy;
- A listing of AEs related to LGX818;
- A listing of AEs related to MEK162;
- A listing of AEs related to Combo Target Therapy;
- A listing of all SAEs;
- A listing of all AEs leading to death;
- A listing of AEs leading to hospitalization;
- A listing of AEs leading to study withdrawal;
- A listing of AESIs.

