4.4. DESCRIPTION OF THE STUDY FLOW

The study will be conducted according to an open-label, prospective, randomized, phase II design.

Randomization will be stratified according to stage arranged in the 3 following strata:

- IIIb/c – M1a – M1b;
- M1c with normal LDH (≤ 2 ULN);

- M1c with elevated LDH (> 2 ULN).

All screening/baseline assessments as outlined in Tables 1 of the protocol (arm A), 2 (arm B) and 3 (arm C) of the Study Protocol must be performed within 28 days prior to the first administration of study drugs on Day 1. Results of tests or examinations performed as standard of care before obtaining informed consent and within the 28 days prior to commencing study drugs may be used. All assessments during the study must be performed within a window +/-3 days of the day indicated on the schedule of assessment, except for tumor evaluations for which a window of +/- 7 days will apply and for Combo Immuno visits for which a window of +/- 2 days will apply.

Eligibility for the study will be determined by the Investigator from the mandatory screening/baseline assessments performed during screening and according to the study inclusion/exclusion criteria.

First dosing of study drugs will be determined by the patient's eligibility and the laboratory assessments done on Day 1 prior to dosing.

Hematology and biochemistry assessments do not need to be repeated on Day 1 if performed within 7 days; if it is necessary to repeat these blood tests, the results must be known before the patient receives treatments to ensure inclusion/exclusion criteria related to these tests are met. Test for HIV infection is mandatory at screening.

Subject Re-enrollment: This study permits the re-enrollment of patients that was not randomized within 28 from ICF signature, after obtaining agreement from the medical monitor prior to re-enrolling a subject. If authorized to re-enrollment, the patient must be re-consented and the same subject-code can be used.

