7. DEFINITION OF ANALYSIS SETS AND SUBGROUPS

Agreement and authorization of patients included/excluded from each analysis set will be performed on a case-by-case basis before the database lock.

The following analysis sets have been defined for this study:

Enrolled Analysis Set [ENR]

The all patients enrolled (ENR) set contains all patients who provided informed consent for this study.

Intent-to-Treat set [ITT]

The Intent-to-Treat (ITT) set will contain all randomized patients. Subjects in the ITT population will be analysed in the treatment group to which they were assigned by the randomization schedule, regardless of which study drug they receive.

The analysis of primary and secondary variables will be carried out in the ITT set.

Safety Analysis Set [SAF]

The Safety Analysis set (SAF) will contain all randomized subjects who received at least one dose of study medication. Subjects in the SAF will be analysed in the treatment group for the study drug they actually received.

The analysis of safety will be carried out in the safety population. If there is any doubt whether a subject was treated or not, they will be assumed treated for the purposes of analysis.

Per Protocol Analysis Set [PP]

The Per Protocol Analysis set (PP) will contain all randomized subjects who did not report any major protocol deviations (as detailed [Paragraph 6](#)).

The analysis on the primary variable (OS) will be repeated in the PP.

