Number of SAEs related to Combo LGX818	n	xx	xx	xx
Number of SAEs related to Combo MEK162	n	xx	xx	xx
Number of SAEs related to Combo Target Therapy	n	xx	xx	xx
Number of AEs leading to hospitalization	n	xx	xx	xx
Number of AEs leading to death	n	xx	xx	xx
Number of AEs leading to withdrawal from the study	n	xx	xx	xx
Number of AEs of special interest (AESI)	n	xx	xx	xx
Number of Patients with at Least One AE	n (%)	xx (xx.x%)	xx (xx.x%)	xx (xx.x%)
Number of Patients with at Least One non-serious AE	n (%)	xx (xx.x%)	xx (xx.x%)	xx (xx.x%)
Number of Patients with at Least One AE related to Ipilimumab	n (%)	xx (xx.x%)	xx (xx.x%)	xx (xx.x%)
Number of Patients with at Least One AE related to Nivolumab	n (%)	xx (xx.x%)	xx (xx.x%)	xx (xx.x%)
Number of Patients with at Least One AE related to Combo Immuno Therapy	n (%)	xx (xx.x%)	xx (xx.x%)	xx (xx.x%)
Number of Patients with at Least One AE related to LGX818	n (%)	xx (xx.x%)	xx (xx.x%)	xx (xx.x%)
Number of Patients with at Least One AE related to MEK162	n (%)	xx (xx.x%)	xx (xx.x%)	xx (xx.x%)
Number of Patients with at Least One AE related to Combo Target Therapy	n (%)	xx (xx.x%)	xx (xx.x%)	xx (xx.x%)
Number of Patients with at Least One serious AE (SAE)	n (%)	xx (xx.x%)	xx (xx.x%)	xx (xx.x%)
Number of Patients with at Least One SAE related to Ipilimumab	n (%)	xx (xx.x%)	xx (xx.x%)	xx (xx.x%)
Number of Patients with at Least One SAE related to Nivolumab	n (%)	xx (xx.x%)	xx (xx.x%)	xx (xx.x%)
Number of Patients with at Least One SAE related to Combo Immuno Therapy	n (%)	xx (xx.x%)	xx (xx.x%)	xx (xx.x%)
Number of Patients with at Least One SAE related to Combo LGX818	n (%)	xx (xx.x%)	xx (xx.x%)	xx (xx.x%)
Number of Patients with at Least One SAE related to Combo MEK162	n (%)	xx (xx.x%)	xx (xx.x%)	xx (xx.x%)
Number of Patients with at Least One SAE related to Combo Target Therapy	n (%)	xx (xx.x%)	xx (xx.x%)	xx (xx.x%)
Number of Patients with at Least One AE leading to hospitalization	n (%)	xx (xx.x%)	xx (xx.x%)	xx (xx.x%)
Number of Patients with at Least One AE leading to withdrawal from the study	n (%)	xx (xx.x%)	xx (xx.x%)	xx (xx.x%)
Number of Patients with at Least One AESI	n (%)	xx (xx.x%)	xx (xx.x%)	xx (xx.x%)

Note: a) Percentages are calculated relative to the total number of patients in the SAF population by treatment arm.

b) An AE is defined as "related" to a study drug if relationship is "Certain", "Probable" or "Possible" to that specific drug. Missing data were considered as Related.

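### AE tables count every event from informed consent, so new events before the first dose are reported under the treatment arms

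*Supplement*

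**What the plan says.** SAP section 21.1 sets the counting window by consent: events "experienced by the patient on or after the informed consent date will be considered in the analysis". It then states that "there will not be derivation to Treatment-emerged Adverse Events (TEAE) and not TEAE". This is an explicit rule, not an omission.

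The denominator is set by exposure. All safety outputs use the Safety Analysis Set (section 21), which under section 7 "will contain all randomized subjects who received at least one dose of study medication". Presentation is by sequence: "The following frequency distributions of adverse events will be provided by treatment arm".

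Section 4.4 shows how much time can lie between consent and first dose. Screening assessments "must be performed within 28 days prior to the first administration of study drugs on Day 1", and the plan allows "re-enrollment of patients that was not randomized within 28 from ICF signature" (the unit is missing and is read here as days).

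For causality, section 21.1 says "An AE will be defined “Related” if causality is “Certain”, “Probable” or “Possible". The related-event shells in section 26 add a rule that section 21.1 does not contain: "Missing data were considered as Related".

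**The concern.** The numerator starts at consent, while the denominator is defined by having received study drug. An event that began before the first dose cannot have been caused by that drug, yet it is tabulated under Arm A, B or C. Each patient counts once per preferred term, so in the summary tables a pre-dose event looks the same as a first event on treatment.

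Section 3.3 names toxicity of the investigational products and the safety of the sequences as what is to be evaluated. Readers will take the arm-level percentages as rates on treatment. At stake is the absolute incidence of individual terms, serious events, hospitalisations and events of special interest. Less common terms are the most sensitive, because a few extra patients move them proportionately more.

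**Working it through.** **1. Does anything else in the SAP remove pre-dose events?** The adverse event shells (Tables 45 to 57 as numbered on the shells) have arm columns only. They have no pre-dose row or column and no footnote limiting events by start date. Listings 54 to 65 show start dates but no pre-dose flag. Nothing found mends the rule.

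**2. How does the SAP treat other data?**

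| Data | Anchor | Place |
|---|---|---|
| Baseline values | last value before first administration of each treatment scheme | section 8.1 |
| Medications | split into prior and concomitant at first dose, with a partial-date algorithm | section 18, Appendix 2 |
| Exposure | first-dose date already derived | section 19 |
| Adverse events | consent, no split at first dose | section 21.1 |

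**3. Length of the pre-dose window.** 28 days / 7 = 4 weeks, as a nominal figure. It can be shorter, because section 4.4 accepts standard-of-care tests done before consent. It can be longer, because section 4.4 gives no limit from randomization to first dose. Re-enrolled patients are also re-consented and may keep their subject code, and section 21.1 does not say which consent date then applies.

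**4. Which tables are affected?**
- All-causality AE, SAE, hospitalisation and AESI tables: yes, for patients who were later dosed.
- Drug-related tables: largely protected by the causality filter. A pre-dose event with blank causality would still enter them under the shell rule.
- Withdrawal table: only an event that began before dosing and led to withdrawal after dosing. A patient withdrawn before dosing is outside the Safety Analysis Set.

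**5. Illustrative size.** The documents give no pre-dose rate, so the inputs here are assumptions. Let p be the true on-treatment incidence of a term and q the proportion of dosed patients with the same term before dosing. Under independence:

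reported incidence = 1 − (1 − p)(1 − q)

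With p = 5%:
- q = 1%: 1 − 0.95 × 0.99 = 5.95%, or about 6.0%
- q = 2%: 1 − 0.95 × 0.98 = 6.9%
- q = 5%: 1 − 0.95 × 0.95 = 9.75%, or about 9.8%

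With 69 patients planned per arm, the excess is 69 × 0.0095 = 0.7 patients at q = 1% and 69 × 0.0475 = 3.3 patients at q = 5%.

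Independence matters. At q = 5%, if the same patients have the term before and during treatment, the reported figure stays at 5%. If no patient has it in both periods, the figure is 5% + 5% = 10%.

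The row for at least one AE of any kind hardly moves: with p = 95% and q = 5%, 1 − 0.05 × 0.95 = 95.25%.

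**The case against.** The strongest reply is that this is a disclosed choice and not an error. The rule is stated openly, and the tables are titled as incidence of adverse events, not treatment-emergent events, so the counts match their labels. It applies identically in all arms, and section 8.3 plans no comparative tests. Separate preferred-term tables restricted to related events already address drug toxicity. Protocol version 10.0 was not available, so any rationale or window rule in it could not be checked. All of this stands. It limits the point to absolute incidence and to a low priority, but it does not align the consent-based count with the stated objective of evaluating toxicity.

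A reader might infer more than the documents support:
- **That events cannot be assigned to a treatment block.** They can. Listing 54 carries event start and end dates, and Listing 42 carries therapy dates by product. A flag keyed to the first study dose would not separate later blocks in any case.
- **That withdrawals are materially inflated.** Patients who withdrew before dosing are not in the analysis set.
- **That symptoms already present at screening are swept in.** Section 13 records ongoing conditions as concomitant diseases, and nothing says that conditions present at consent are entered as adverse events. New events after consent are what is mixed in.
- **That inflation is large, for example from 20% to 28%.** That needs 10% of patients to report the same new term in about four weeks, as well as independence. The documents give no basis for either.

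**Conclusion.** The point holds as a modest reporting weakness. New events between consent and first dose, in patients who go on to be dosed, are counted under the arms in the all-causality AE, SAE, hospitalisation and AESI tables. The drug-related tables are mostly protected, apart from blank causality. The direction is a slight overstatement of absolute incidence at preferred-term level. It is expected to be similar across arms, so it should not change how the sequences compare.

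The size cannot be determined from the documents. The reading of 6.0% to 9.8% for a true 5% rests on an assumed pre-dose frequency of 1% to 5% for that term and on independence; overlap within patients would reduce it. Acting on this is worthwhile because it is cheap, not because it threatens the trial's conclusions.

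**What to change.** In section 21.1, replace the statement that no split will be made with a derived treatment-emergent flag: onset, or worsening, on or after the first study dose as already defined in section 19. Base the AE, SAE, hospitalisation and AESI tables on flagged events, footnote the rule in the shells, and give pre-dose events of dosed patients their own listing. For a withdrawal after dosing caused by an event that began before it, a footnote is enough. State the missing-causality rule in section 21.1 so that text and shells agree.

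Partial onset dates need a convention, because section 9.3 rules out imputation and Appendix 2 covers medications only. Treating an event as emergent when in doubt is conservative.

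No new data are needed for onset: event start dates are in Listing 54 and therapy start dates in Listing 42. For worsening, Listing 54 has a single grade column, and the documents do not say whether a change of grade opens a new record; this should be confirmed. The cost is one extra derivation and slightly lower counts. If the sponsor wants to keep the consent-based tables, a parallel treatment-emergent set would also answer the point.

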4.2. SAMPLE SIZE

This study was designed as a phase II, randomized trial with no formal comparative test. The sample size was discussed for the primary endpoint Overall Survival (OS).

For each arm a single-stage design as described by A'Hern (A'Hern, 2001) was used.

A median PFS of about 10 months for the combo target therapy (LGX818/MEK162) was assumed (Mc Arthur et al, 2013) and a similar value for the combo immunotherapy (ipilimumab/nivolumab) derived from the aggregate clinical activity rate of 65% (Wolchock et al, 2013) which, using an exponential distribution for PFS, could broadly give a median PFS of about 9.5 months. OS seems to be strictly correlated with total PFS.

The null hypothesis was a median OS time of 15 months (i.e. percentage of surviving patient of 33% at 24 months). The alternative hypothesis was a median OS time of 23 months (i.e. percentage of surviving of 48% at 24 months).

Using an exact 5% one-sided significance test, at least 69 patients would have to be randomized in each treatment arm when the power of the study is 80%.

For each arm the strategy would be further investigated if at least 30 patients, alive at 24 months, were observed.

Taking into account a 10% drop-out rate, a total of 230 patients would be enrolled to ensure a minimum of 207 randomized patients.

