Subjects will be assessed for response by computed tomography (CT) or Magnetic Resonance Imaging (MRI). All measurable and non-measurable lesions must be documented at screening (within 28 days prior to randomization) and re-assessed at each subsequent tumor evaluation (every 8 weeks (+/- 1 week) for the first year, every 12 weeks (+/- 1 week) while the patient is on study). Tumor assessments with CT or MRI scans of the brain, chest, abdomen, and pelvis will be performed until disease progression after the second combo treatment per RECIST v1.1.

For patients who discontinue study treatment for reason other than investigator-determined disease progression, tumor assessments should continue to be performed as scheduled.

Patients will continue to be on study and can be switched to the subsequent therapy after PD as per protocol in both arm A and B.

In case of an interruption of the treatment in arm C, reason other than investigator-determined disease progression, during the first 8 weeks (2 cycles of therapy), patient can continue the study treatment with combo immuno, as scheduled.

For patients with palpable/superficial lesions, clinical disease assessments by physical examination should be performed at baseline and throughout study treatment as clinically indicated. Color photographs with ruler/calipers will be taken at baseline and at all subsequent tumor assessment time points.

The National Cancer Institute Common Toxicity Criteria for Adverse Events (NCI CTC-AE) Version 4.03 will be used to evaluate the clinical safety of the treatment in this study. Patients will be assessed for AEs at each clinical visit and as necessary throughout the study.

Biomarker study

A correlative biological study will be performed for the evaluation of biomarkers on the biological sample available (paraffin-embedded tissue, frozen tissue, blood, serum, etc.). Approximately 80-90 patients will take part in the biomarker study.

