Source: XXXX.SAS, Run on DDMMYYYY

TABLE 46. Incidence of AEs by primary System Organ Class and Preferred Term

POPULATION: SAF

	Statistic	Arm A (N = XX)	Arm B (N = XX)	Arm C (N = XX)
<Primary SOC>	n (%) E	xx (xx.x%) xx	xx (xx.x%) xx	xx (xx.x%) xx
<PT>	n (%) E	xx (xx.x%) xx	xx (xx.x%) xx	xx (xx.x%) xx
<PT>	n (%) E	xx (xx.x%) xx	xx (xx.x%) xx	xx (xx.x%) xx
<PT>	n (%) E	xx (xx.x%) xx	xx (xx.x%) xx	xx (xx.x%) xx
<Primary SOC>	n (%) E	xx (xx.x%) xx	xx (xx.x%) xx	xx (xx.x%) xx
<PT>	n (%) E	xx (xx.x%) xx	xx (xx.x%) xx	xx (xx.x%) xx
<PT>	n (%) E	xx (xx.x%) xx	xx (xx.x%) xx	xx (xx.x%) xx
<PT>	n (%) E	xx (xx.x%) xx	xx (xx.x%) xx	xx (xx.x%) xx
<Primary SOC>	n (%) E	xx (xx.x%) xx	xx (xx.x%) xx	xx (xx.x%) xx
<PT>	n (%) E	xx (xx.x%) xx	xx (xx.x%) xx	xx (xx.x%) xx
<PT>	n (%) E	xx (xx.x%) xx	xx (xx.x%) xx	xx (xx.x%) xx
<PT>	n (%) E	xx (xx.x%) xx	xx (xx.x%) xx	xx (xx.x%) xx
<Primary SOC>	n (%) E	xx (xx.x%) xx	xx (xx.x%) xx	xx (xx.x%) xx
<PT>	n (%) E	xx (xx.x%) xx	xx (xx.x%) xx	xx (xx.x%) xx
<PT>	n (%) E	xx (xx.x%) xx	xx (xx.x%) xx	xx (xx.x%) xx
<PT>	n (%) E	xx (xx.x%) xx	xx (xx.x%) xx	xx (xx.x%) xx

Note: a) Percentages are calculated relative to the total number of patients in the SAF Population by treatment arm.

b) Each patient is counted at most once within each SOC and PT.

c) AEs were coded using MedDRA version 20.0.

d) n = number of patients, E = number of events.

Source: XXXX.SAS, Run on DDMMYYYY

TABLE 47. Incidence of Ipilimumab-related AEs by primary System Organ Class and Preferred Term

POPULATION: SAF

	Statistic	Arm A (N = XX)	Arm B (N = XX)	Arm C (N = XX)
<Primary SOC>	n (%) E	xx (xx.x%) xx	xx (xx.x%) xx	xx (xx.x%) xx
<PT>	n (%) E	xx (xx.x%) xx	xx (xx.x%) xx	xx (xx.x%) xx
<PT>	n (%) E	xx (xx.x%) xx	xx (xx.x%) xx	xx (xx.x%) xx
<PT>	n (%) E	xx (xx.x%) xx	xx (xx.x%) xx	xx (xx.x%) xx
<Primary SOC>	n (%) E	xx (xx.x%) xx	xx (xx.x%) xx	xx (xx.x%) xx
<PT>	n (%) E	xx (xx.x%) xx	xx (xx.x%) xx	xx (xx.x%) xx
<PT>	n (%) E	xx (xx.x%) xx	xx (xx.x%) xx	xx (xx.x%) xx
<PT>	n (%) E	xx (xx.x%) xx	xx (xx.x%) xx	xx (xx.x%) xx
<Primary SOC>	n (%) E	xx (xx.x%) xx	xx (xx.x%) xx	xx (xx.x%) xx
<PT>	n (%) E	xx (xx.x%) xx	xx (xx.x%) xx	xx (xx.x%) xx
<PT>	n (%) E	xx (xx.x%) xx	xx (xx.x%) xx	xx (xx.x%) xx
<PT>	n (%) E	xx (xx.x%) xx	xx (xx.x%) xx	xx (xx.x%) xx
<Primary SOC>	n (%) E	xx (xx.x%) xx	xx (xx.x%) xx	xx (xx.x%) xx
<PT>	n (%) E	xx (xx.x%) xx	xx (xx.x%) xx	xx (xx.x%) xx
<PT>	n (%) E	xx (xx.x%) xx	xx (xx.x%) xx	xx (xx.x%) xx

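### AE tables give only crude percentages and event counts over a window whose length depends on how long the sequence works, so arms cannot be read across at equal time at risk

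*Supplement*

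**What the plan says.** Section 4.4 has AEs collected for as long as the patient is followed: "Patients will be assessed for AEs at each clinical visit and as necessary throughout the study". Section 21.1 counts every AE "experienced by the patient on or after the informed consent date will be considered in the analysis", and states that "there will not be derivation to Treatment-emerged Adverse Events (TEAE) and not TEAE". The SAP text gives no end to the window.

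The summary measure in 21.1 is "Counts and percentages will be presented by primary System Organ Class (SOC) and Preferred Term (PT"), by treatment arm. In the overview shell (Table 45) the entries are numbers of events and numbers of patients, and "Percentages are calculated relative to the total number of patients in the SAF population by treatment arm". The SOC/PT shells (Tables 46-57) carry three quantities per cell, patients, percentage and events, with the key "n = number of patients, E = number of events" and the same arm-wide denominator. (These are the numbers printed on the shells; the contents list in section 26 numbers the same tables 43-55.)

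Under section 4.3 each combination is given until progression and is followed by the next one, also until progression. The exception is Arm C's first targeted block, fixed at 8 weeks. Exposure in weeks is summarised in a separate table (section 19, shell Table 23) and is not linked to any AE table. No rate per patient-time, time-to-first-event estimate, common window or by-block AE table is planned.

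**The concern.** Crude percentages and counts depend on two things: how often harm occurs per unit of time, and how long patients are watched. Here the second is partly a result of the sequence. A sequence that delays progression and death keeps patients on drug and under AE assessment longer, and gathers more events at the same rate of harm.

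Toxicity is among the objectives on which section 3.2 sets out to evaluate the three sequences, and the primary objective is to define the best one. The arms stand in adjacent columns, so the AE tables will be read as a comparison even though nothing is tested. The plan allows for unequal follow-up in OS, total PFS and DoR through Kaplan-Meier estimates with censoring; the AE summaries have no counterpart. A benefit-risk reading could therefore mistake longer observation for greater toxicity, or miss a lower rate of harm.

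**Working it through.** **Inputs from the SAP (section 4.2).** Median OS is 15 months under the null and 23 months under the alternative. The plan links survival to time on the sequence: "OS seems to be strictly correlated with total PFS". The longest landmark anywhere in the plan is 3 years.

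**The plan's own figures first.** With exponential survival, 24-month survival is 0.5^(24/15) = 0.330 and 0.5^(24/23) = 0.485, against the plan's 33% and 48%. With n = 69 and a cut-off of 30, the exact binomial tail is 0.0446 at 33% and 0.808 at 48%, and 207/0.9 = 230. The design reproduces, and the exponential form used below agrees with the plan's own percentages.

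**Assumptions not in the documents.** AE observation follows the two survival curves; it is capped at T = 36 months; the AE rate λ is constant and identical in both arms. No AE rate is given, so a range is shown.

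**Formulas.** With μ = ln 2/median (0.0462 and 0.0301 per month):
- mean observed time = (1 − exp(−μT))/μ
- events per 100 patients = 100 × λ × mean observed time
- proportion with at least one event = λ/(λ+μ) × (1 − exp(−(λ+μ)T))

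**Mean observed time.** Capped: 17.5 v 22.0 months, ratio 1.25. Uncapped: 21.6 v 33.2 months, ratio 1.53.

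**Worked case, 0.3 per year (λ = 0.025 per month), capped.**
- 15-month arm: 0.025/0.0712 × (1 − exp(−2.564)) = 0.351 × 0.923 = 32.4%
- 23-month arm: 0.025/0.0551 × (1 − exp(−1.985)) = 0.453 × 0.863 = 39.1%
- Events per 100 patients: 2.5 × 17.54 = 43.9 v 2.5 × 21.97 = 54.9

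| True rate, both arms | 36-month cap: % with event | Uncapped: % with event |
|---|---|---|
| 0.1 per year | 13% v 16% | 15% v 22% |
| 0.3 per year | 32% v 39% | 35% v 45% |
| 0.5 per month | 91.5% v 94.3% | 91.5% v 94.3% |

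Uncapped, 0.3 per year gives 54 v 83 events per 100 patients.

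**The same data as a rate.** Per 100 patients, capped person-time is 100 × 17.54/12 = 146.2 and 100 × 21.97/12 = 183.1 patient-years. Then 43.9/146.2 and 54.9/183.1 both equal 30 events per 100 patient-years, and the spurious difference disappears.

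**Break-even.** The longer-observed arm could have a true rate 1 − 17.54/21.97 = 20% lower (35% lower uncapped) and still show as many events.

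**Where the direction can reverse.** Suppose the first block has a median of 10 months (the plan's figure for targeted therapy) against an illustrative 20. By 24 months, 1 − 0.5^(24/10) = 81% v 1 − 0.5^(24/20) = 56% of patients would have left it, ignoring death before progression. With the whole arm as denominator, the arm with the longer first block would show fewer AEs related to the second combination.

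**The case against.** The strongest defence is that this is a non-comparative phase II trial. Section 8.3 rules out tests between arms, no safety decision rule exists, and crude incidence beside an exposure table is a recognised descriptive format. A reader can divide the events in Table 45 by mean exposure in Table 23 and get a rough rate, and the listings carry AE dates.

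Part of this stands: no formal inference is affected, and the raw material is planned. But the two tables do not fit together. Exposure runs from first to last dose, whereas AEs count from consent; the Table 23 shell is labelled ITT, whereas section 19 and the AE tables use the safety set. First-event rates and incidence in a common window cannot be recovered from them. The protocol, which is not shown, may end AE collection a set time after the last dose; the window would still depend on treatment duration.

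A reader might infer that every AE table will make the best sequence look the most toxic. The documents do not support that. Part of each sequence has a planned length (Arm C's first block, and four doses of the ipilimumab combination in all arms). Tables 47-52 concern drug- or combination-related AEs, where the direction can reverse, as it can for Table 57 on AEs leading to death. True differences between arms can also outweigh the effect. Nor do the documents support taking the uncapped figures as the expected size: they require AE observation until every patient has died, which the SAP does not state.

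**Conclusion.** The point holds as a limitation of the planned safety summaries. The crude measures mix the rate of harm with the length of observation, and nothing in the SAP separates them. At equal underlying rates, the longer-lasting sequence tends to show more events and, for events of intermediate frequency, more affected patients. At 0.3 per year with a 36-month cap, the artefact is about 7 percentage points and 11 events per 100 patients; at 0.1 per year it is about 3 points. For very common early AEs it is under 3 points. These sizes rest on windows following the 15 and 23 month medians, a constant and equal AE rate, and rates chosen for illustration. The primary OS analysis is untouched. This is a cheap improvement that should be made, not a flaw that invalidates the safety tables.

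**What to change.** Keep the crude tables and make these additions to section 21.1 and the shells:

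1. For the all-AE, SAE and AESI rows, add by arm the number of events and of first events per 100 patient-years of AE observation. Define that observation time (start and end) in 21.1, consistently with the protocol.
2. As a supplement for the same rows, give cumulative incidence of first event at a fixed time from first dose, such as 24 months, with death as a competing event.
3. For drug- or combination-related rows, use as denominator only patients who started that combination, and count their time from its start. A window from first dose would largely compare first blocks here and should not be used.
4. State in 21.1 that whole-study crude counts and percentages are not to be read across arms without these rates.

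The dates needed (AE onset, dosing, death or last contact) are already in the planned listings, so the cost is a few extra columns and some programming. The drawback is that person-time rates assume a roughly constant hazard, which is why the fixed-time incidence is shown beside them.
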